2.1.3.9 Windows for multiple assessments

In order to summarize data collected over time (including unscheduled visits), the assessments will be time slotted. The following general rule will be applied in creating the assessment windows: If more than one assessment is available in the same time window, the assessment closest to the planned date will be used. If 2 assessments within a time window are equidistant from the target date, then the earlier of the 2 assessments will be used. If there are multiple assessments on the same date, then the worst case will be used.

The following tables define time windows for descriptive summary of PRO ([Table 2-1](#) to [Table 2-4](#)) and ECOG performance status (Table 2-1) data by visit and longitudinal data analysis planned in [Section 2.11](#).

Table 2-1 Time windows for ECOG PS

Assessment	Target study day of assessment	Time interval
Baseline	≤ 1	≤ Study days 1
Cycle 2 Day 1	22	Study days 2 to 32
Cycle 3 Day 1	43	Study days 33 to 53
Cycle k Day 1 (k≥ 4)	d=(k-1)×21+1	Study days d-10 to d+10
		For last cycle of dosing: from (k-1)×21-9 to EOT disposition date + 7 days
		Note: EOT visit data are included if obtained within 7 days of

Assessment	Target study day of assessment	Time interval
Safety follow-up	EOT + 30	permanent discontinuation of study treatment. From EOT disposition date + 8 days to 44 days after the EOT disposition date

Table 2-2 Time windows for PRO: NSCLC-SAQ, [REDACTED], [REDACTED], [REDACTED]

Time window	Planned visit timing	Time window definition
Baseline	$\leq 1^*$	\leq Study day 1^*
On treatment		
Cycle 1 Day 8	8	Study days 2 – 11
Cycle 1 Day 15	15	Study days 12 – 18
Cycle 2 Day 1	22	Study days 19 – 25
Cycle 2 Day 8	29	Study days 26 – 32
Cycle 2 Day 15	36	Study days 33 – 39
Cycle 3 Day 1	43	Study days 40 – 46
Cycle 3 Day 8	50	Study days 47 – 53
Cycle 3 Day 15	57	Study days 54 – 60
Day 1 of every cycle from Cycle 4		
Cycle 4 Day 1	64	Study days 61 – 74
Cycle 5 Day 1	85	Study days 75 – 95
Cycle k Day 1 ($k = 4, 5, \dots$)	$d = (k-1) \times 21 + 1$	Study days $(k-1) \times 21 - 9$ to $(k-1) \times 21 + 11$ For last cycle of dosing: from $(k-1) \times 21 - 9$ to EOT disposition date +7 Note: EOT visit data are included if obtained within 7 days of permanent discontinuation of study treatment.
Post treatment		
Efficacy follow-up, every 12 weeks		
Efficacy follow-up 1	12 weeks after EOT disposition date + 7 days	From EOT disposition date + 8 days to 18 weeks after EOT disposition date + 7 days
Efficacy follow-up 2	24 weeks after 24 weeks after EOT disposition date + 7 days	From 18 weeks after EOT disposition date + 8 days to 30 weeks after EOT disposition date + 7 days
Efficacy follow-up k ($k = 3, 4, \dots$) ^{\$}	$12 + (k-1) \times 12$ weeks after EOT disposition date + 7 days	From $(k-1) \times 12 + 6$ weeks after EOT disposition date + 8 days to $(k-1) \times 12 + 18$ weeks after EOT disposition date + 7 days

Time window	Planned visit timing	Time window definition
Post disease progression		
Survival follow-up 1	12 weeks after disease progression date	From PD date [#] to 18 weeks after PD date [#]
Survival follow-up 2	24 weeks after disease progression date	From 18 weeks after PD date [#] + 1 day to 30 weeks after PD date [#]
Survival follow-up 3	36 weeks after disease progression date	From 30 weeks after PD date [#] + 1 day to 42 weeks after PD date [#]
Survival follow-up k if available (k = 4, 5, ...)	12×k weeks after disease progression date	From 12×k-6 weeks after PD date [#] + 1 day to 12×k + 6 weeks after PD date [#]

* Study day 1 = date of first treatment, C1D1

Post treatment study day 1 = end of treatment date + 1 day

\$ The assessment “at disease progression” in efficacy follow-up should be the last visit in this period

It is the EOT visit date + 8 days for participants without efficacy follow-up

Table 2-3 Time windows for PROs: EORTC QLQ-C30

[figure not shown]
Time window	Planned visit timing	Time window definition
Baseline	On or before Study Day 1*	≤ Study Day 1*
On treatment		
Cycle 2 Day 1	Study Day 22	Study Days 2 – 32
Cycle 3 Day 1	Study Day 43	Study Days 33 – 53
Cycle k Day 1 (k≥ 4)	Study day d=(k-1)×21+1	Study days d-10 to d+10 For last cycle of dosing: from (k-1)×21-9 to EOT disposition date + 7 days Note: EOT visit data are included if obtained within 7 days of permanent discontinuation of study treatment.
Post treatment		
Efficacy follow-up, every 12 weeks		
Efficacy follow-up 1	12 weeks after EOT disposition date + 7 days	From EOT disposition date + 8 days to 18 weeks after EOT disposition date + 7 days
Efficacy follow-up 2	24 weeks after EOT disposition date + 7 days	From 18 weeks after EOT disposition date + 8 days to 30 weeks after EOT disposition date + 7 days
Efficacy follow-up k (with k = 3, 4, ...)	12+(k-1)×12 weeks after EOT disposition date + 7 days	From (k-1)×12+6 weeks after EOT disposition date + 8 days to (k-1)×12+18 weeks after EOT disposition date + 7 days

Time window	Planned visit timing	Time window definition
After disease progression		
Follow-up 1 after disease progression	12 weeks after disease progression date	From PD date [#] to 18 weeks after PD date [#]
Follow-up 2 after disease progression	24 weeks after disease progression date	From 18 weeks after PD date [#] + 1 day to 30 weeks after PD date [#]
Follow-up 3 after disease progression	36 weeks after disease progression date	From 30 weeks after PD date [#] + 1 day to 42 weeks after PD date [#]
Follow-up k after disease progression (k = 4, 5, ...)	12×k weeks after disease progression date	From 12×k-6 weeks after PD date [#] + 1 day to 12×k+6 weeks after PD date [#]

* Study Day 1 = date of first treatment, C1D1

Post treatment study day 1= end of treatment date + 1 day

It is the EOT visit date + 8 days for participants without efficacy follow-up

2.1.3.10 Last contact date

The last contact date will be derived for participants not known to have died at the analysis cut-off using the last complete date among the following:

Table 2-5 Last contact date

Source data	Conditions
Last contact date/last date participant was known to be alive from Survival Follow-up page	Participant status is reported to be alive, lost to follow-up or unknown
Start/End dates from further antineoplastic therapy	Non-missing medication/procedure term.
Start/End* dates from drug administration record	Non-missing dose. Doses of 0 are allowed.
End of treatment date from end of treatment page	No condition.
Tumor assessment date	Evaluation is marked as 'done'.
Laboratory/PK collection dates	Sample collection marked as 'done'.
Vital signs date	At least one non-missing parameter value
Performance Status date	Non-missing performance status
Start/End dates of AE	Non-missing verbatim term

The last contact date is defined as the latest complete date from the above list on or before the data cut-off date. The cut-off date will not be used for last contact date, unless the participant was seen or contacted on that date. Completely imputed dates (e.g. the analysis cut-off date programmatically imputed to replace the missing end date of a dose administration record) will not be used to derive the last contact date. Partial date imputation is allowed for event (death)/censoring is coming from 'Survival information' eCRF.

The last contact date will be used for censoring of participants in the analysis of overall survival.

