7.1.3 Overall Survival

All participants will enter the survival follow-up period once they complete the safety follow-up and efficacy follow-up after treatment discontinuation (whichever is longer). Survival status will be collected every 12 weeks (+/- 14 days) regardless of treatment discontinuation reason (except if consent is withdrawn or participant is lost to follow-up) until death, lost to follow-up, or withdrawal of consent for survival follow-up.

[figure not shown]
Additional survival assessments may be performed outside the 12-week follow-up schedules if a survival update is required due to safety or regulatory needs.

Survival information can be obtained via phone, and information will be documented in the source documents and relevant eCRFs. Information on the therapies received for NSCLC, if

any, after study treatment has been completed will be collected. All SAEs reported during this time period must be reported as described in Section 8.7.

Figure 7-1 illustrates study flow.

Figure 7-1 **Study Flow**

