2.1.1 Data included in the analysis

Data from all participants who signed the main informed consent will be used in the analysis. Data collected after participants' withdrawal of informed consent for further participation in the study will not be reported (except for death date, if it is obtained from public records [registers], local law and participant informed consent permitting). The date on which a participant withdraws full consent is recorded in the eCRF.

A cut-off date will be established for the primary analysis after the participants in the respective cohort who are still receiving study treatment will have completed at least 4 tumor assessments or discontinued study treatment earlier. If this criterion is reached earlier in one of the cohorts, the cut-off date and the primary analysis may occur at different times.

All statistical analyses will be performed using all data collected in the database up to the data cut-off date (per cohort, if applicable). All data with an assessment date or event start date (e.g. vital sign assessment date or start date of an adverse event) prior to or on the cut-off date will be included in the analysis. Any data collected beyond the cut-off date will not be included in the analysis and will not be used for any derivations.

All events with start date before or on the cut-off date and end date after the cut-off date will be reported as ‘ongoing’. The same rule will be applied to events starting before or on the cut-off date and not having a documented end date. This approach applies, in particular, to adverse event and concomitant medication reports. For these cases, the end date will not be imputed and therefore will not appear in the listings.

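### If deaths count by event date, the OS rules keep deaths learned after the cut-off but ignore proof of life obtained then, which biases the OS curve downward

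*SAP*

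**What the plan says.** SAP 2.1.3.10 derives a last contact date from a list of sources (survival page, dosing, tumor assessments, laboratory and PK samples, adverse events, later cancer therapy and others): "The last contact date is defined as the latest complete date from the above list on or before the data cut-off date". It then restricts the cut-off date itself: "The cut-off date will not be used for last contact date, unless the participant was seen or contacted on that date". The purpose is explicit: "The last contact date will be used for censoring of participants in the analysis of overall survival". SAP 2.8.1.5 and Protocol 9.4.1.2 both censor OS at the latest date known alive, on or before the cut-off.

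SAP 2.1.1 governs which data enter. Data with an assessment or event start date "prior to or on the cut-off date will be included in the analysis". The next sentence reads: "Any data collected beyond the cut-off date will not be included in the analysis and will not be used for any derivations". After consent withdrawal nothing further is reported, "except for death date, if it is obtained from public records [registers], local law and participant informed consent permitting".

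Protocol 7.1.3 schedules survival contacts every 12 weeks, with a window of 14 days either side. It allows extra survival assessments for safety or regulatory reasons, but does not require one at the primary-analysis cut-off. No OS sensitivity analysis is described.

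**The concern.** Take two participants in survival follow-up, both last contacted eight weeks before the cut-off and both reached again two weeks after it. One is found to have died a month before the cut-off, the other is alive. On the event-date reading, the death enters at its true date. The survivor's eight weeks are removed, although the later contact proves that the participant lived through them. Exposure is lost because a participant survived, so censoring is no longer independent of outcome.

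This affects OS in both cohorts and in the pooled STK11 group, all secondary objectives. In a single-arm study, OS can be read only against outside figures, and a shift that always goes one way does not average out with more participants.

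**Working it through.** The documents give no OS assumption, event count or target, so there is no figure to reproduce. The check covers direction first, then size.

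**Direction.** The Kaplan-Meier estimate is S(t) = product over death times t_i ≤ t of (1 − d_i/n_i). When all deaths up to the cut-off are known, the SAP rule and censoring at the cut-off use the same d_i. The SAP rule removes survivors early, so each n_i is equal or smaller, each factor is equal or smaller, and the curve can never be higher.

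**Inputs from the documents.**
- Cohort sizes 90 and 30 (Protocol 9.9).
- Minimum follow-up about 24 weeks (Protocol 9): 24 × 7 / 30.4375 = 5.5 months.
- Contact every 21 days on treatment (cycle length) and every 84 days ± 14 afterwards (Protocol 7.1.3).

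**Assumptions.**
- Median OS 12.5 months, and median time on treatment 6.3 months (set to median PFS). Protocol 2.2.3 reports both medians for another KRAS G12C inhibitor in pretreated patients.
- Exponential survival and uniform accrual over 9, 12 or 18 months.
- All deaths up to the cut-off are known.

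True 12-month OS is then 0.5^(12/12.5) = 51.4%.

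**Size if every pre-cut-off death counts** (400,000 simulated participants per row):

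| Accrual / minimum follow-up (months) | 12-month OS: SAP rule | Censored at cut-off | Shift (points) | Median: SAP rule | Censored at cut-off | Shift (months) |
|---|---|---|---|---|---|---|
| 9 / 5.5 | 46.9% | 51.4% | −4.5 | 11.25 | 12.49 | −1.24 |
| 12 / 5.5 | 48.8% | 51.3% | −2.5 | 11.64 | 12.46 | −0.82 |
| 18 / 5.5 | 50.1% | 51.4% | −1.3 | 12.03 | 12.50 | −0.47 |
| 18 / 12 | 51.2% | 51.4% | −0.2 | 12.41 | 12.49 | −0.08 |

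In the first three rows, survivors lose on average 29 to 32 days. With a median OS of 18 months, 8 months on treatment and 12 months' accrual, 12-month OS is 61.0% against 62.9%, a shift of −1.9 points.

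**Single trials** (4,000 per size, 12-month accrual). The mean shift at 12 months is −2.5 points at both n = 90 and n = 30. The SAP curve is lower in 100% and 99% of trials, and higher in none. The sampling SD of the 12-month estimate is about 6 and 10 points respectively.

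**Dependence on which late deaths are counted** (12-month OS under the SAP rule, separate simulation, true value 51.4%):

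| Off-treatment deaths after the last scheduled contact | 9-month accrual | 12-month | 18-month |
|---|---|---|---|
| All counted | 46.8% | 48.9% | 50.1% |
| Half counted | 48.8% | 50.0% | 50.7% |
| Only those learned at contacts up to the cut-off | 50.9% | 51.1% | 51.2% |

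The last row leaves 51.4 − 50.9 = 0.5, 51.4 − 51.1 = 0.3 and 51.4 − 51.2 = 0.2 points. A survival sweep within 14 days before the cut-off, with all deaths counted, gives 50.6% to 51.1%, a shift of 0.3 to 0.8 points.

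**The case against.** The strongest answer is that SAP 2.1.1 can be read the other way. It opens by limiting analyses to data collected in the database up to the cut-off and ends by barring anything collected later. A death first learned after the cut-off is also data collected later, and SAP 2.1.3.10 speaks of participants not known to have died at the cut-off. On that reading both kinds of late information are dropped and little bias remains. This stands: a reader might infer that the SAP definitely counts every death up to the cut-off, but the text supports both readings. It does not dispose of the point. The event-date sentence is equally explicit, and deaths reported promptly between scheduled contacts would still enter.

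The contact model is also sparse. Imaging continues after treatment for participants without progression, treatment beyond progression keeps visits frequent, and the last-contact list draws on many sources. The survival and treatment figures come from a different drug in a later line, and accrual duration is assumed. These limits make the size illustrative; they do not change its direction.

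A reader might further infer that withdrawn participants are systematically searched in registers, with only the deaths used. The documents describe no such search. They permit a death date if one is obtained, where law and consent allow. The allowance runs one way, but its effect cannot be sized from the plan.

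Finally, OS carries no hypothesis or threshold, the shift is smaller than the sampling error, and later data will be reported separately. All of this is correct and limits the importance.

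**Conclusion.** The point holds, conditional on the event-date reading of SAP 2.1.1. On that reading the OS curve is biased downward, by about 1.3 to 4.5 points at 12 months and 0.5 to 1.2 months on the median. Those ranges rest on a borrowed 12.5-month median OS, 9 to 18 months' accrual, 5.5 months' minimum follow-up and full ascertainment of deaths. If deaths learned after the cut-off are excluded, about 0.2 to 0.5 points remain. With 12 months' minimum follow-up and 18-month accrual the shift is 0.2 points.

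Two stronger inferences fail. Proof of life on the cut-off date itself is used; only later contacts are ignored. The ORR success and futility rules are untouched. This is a correction worth making to a descriptive secondary endpoint, together with an ambiguity that the SAP should settle.

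**What to change.** - In SAP 2.1.3.10 and 2.8.1.5, add: *A participant documented alive on or after the cut-off date is censored for OS at the cut-off date.* This fits Protocol 9.4.1.2, because proof of life after the cut-off establishes that the participant was alive on it.
- In SAP 2.1.1, add a matching exception limited to vital status, and state that deaths dated on or before the cut-off count whenever they are learned before database lock.
- For participants who withdrew consent, censor OS at withdrawal, at least as a sensitivity analysis, instead of adding register deaths alone. A register-search date should not serve as a last-known-alive date. Absence from a register is not proof of life, SAP 2.1.1 admits only death dates after withdrawal, and Protocol 7.3 treats withdrawal as a request to stop using data.

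The cost is SAP wording, a narrow exception to the data-cut rule, and some extra cleaning of survival contacts dated after the cut-off. Contacts already made before database lock can be used.

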2.2 Analysis sets

Participants are considered to be enrolled into the study if they have signed the main informed consent. Only participants who have signed the main informed consent will be included in the analysis data sets.

Participants who signed a molecular pre-screening informed consent form but failed to meet pre-screening criteria, as well as participants who signed the main informed consent form and were subsequently found to be ineligible (have failed to meet inclusion or exclusion criteria) will be considered screen failures.

Full Analysis Set

The Full Analysis Set (FAS) comprises all participants to whom study treatment has been assigned and who received at least one dose of study treatment. Participants will be analyzed according to the cohort they have been assigned to. Participants may be enrolled based on PD-L1 expression status and the presence of a KRAS G12C mutation and STK11 mutation (cohort B only) determined by a validated local test or a central test in tumor tissue or blood.

Safety Set

The Safety Set includes all participants who received at least one dose of study treatment.

The FAS and Safety Set in this study are identical.

Pharmacokinetic Analysis Set

The Pharmacokinetic Analysis Set (PAS) includes all participants who received at least one planned dose of study treatment and provide an evaluable pharmacokinetic concentration.

The criteria below need to be considered for a concentration to be evaluable:

- Participant did not vomit within 4 hours after dosing of JDQ443
- For all pre-dose samples, PK draw occurred before the next dose intake
- For post-dose PK samples, PK draw with concentration following planned dose
- Any PK blood samples with missing collection date or time, or missing associated study treatment dosing date or time will be excluded

Full Pharmacokinetic Analysis Set

The Full Pharmacokinetic Analysis Set (FPAS) includes PAS participants with extensive PK collection schedule who provide an evaluable PK profile. A profile is considered evaluable if the conditions listed for the PAS and the following conditions are met:

- Participant received the planned dose
- Participant provides at least one valid primary PK parameter

PK blood samples with missing collection date or time or missing associated JDQ443 dosing date or time will be excluded.

Additionally, a PK sample can be considered not evaluable as per scientific judgment of the clinical pharmacology expert. In such case, the PK sample will be excluded from the analyses and the reason for its exclusion will be documented.

2.2.1 Subgroups of interest

No formal statistical test of hypotheses will be performed for the subgroups.

Subgroup 1: Pooled group of participants with STK11 mutation tumors

Participants in the FAS from cohort A and cohort B, whose tumors harbor an STK11 mutation (irrespective if the enrollment was based on local or central testing), will be pooled and analyzed as a subgroup (“STK11 pooled group”). Depending on the number of local-central discordant cases, an additional subgroup may be analyzed with only participants with centrally confirmed mutation.

The endpoints for the secondary objectives for this pooled group will comprise ORR, DOR, DCR, TTR, and PFS by BIRC and local radiology assessment as well as OS.

Subgroup 2: Biomarker subgroups based on KRAS G12C, STK11 and/or PD-L1 status

The following subgroups of the FAS will only be analyzed for cohort A and the STK11 pooled group for efficacy endpoints. Due to the small number of participants in cohort B, subgroup categories are expected to be too small to allow reasonable conclusions.

Cohort A – subgroups based on KRAS G12C mutation status in tissue and blood

- a. Participants with both presence of a KRAS G12C mutation and PD-L1 expression < 1% centrally confirmed in tumor tissue, irrespective of the test type (central versus local) and sample type (blood versus tissue) used for eligibility.
- b. Participants enrolled based on a blood test for KRAS G12C, irrespective if the enrollment was based on local or central testing and irrespective of the retrospective central result.

STK11 pooled group

- c. Participants with the presence of both a KRAS G12C and a STK11 mutation centrally confirmed in tumor tissue, irrespective of the test type (central versus local) and sample type (blood versus tissue) used for KRAS G12C status determination for eligibility.
- d. Participants with a STK11 mutation who enrolled based on a blood test for KRAS G12C, irrespective of local or central testing and irrespective of the retrospective central result.

The endpoints for subgroup 2a-2d will comprise ORR, DOR, DCR, TTR, and PFS by BIRC and local radiology assessment as well as OS.

Analyses of additional subgroups based on the biomarkers may be included in the CSR or provided outside of the CSR, if deemed appropriate.

Subgroup 3: Chinese and non-Chinese participants

PK data will be analyzed separately for Chinese participants, i.e. participants from sites in China, and non-Chinese, from all other sites (see [Section 2.10](#)).

Subgroup 4: Baseline characteristics subgroups for efficacy

Analyses for subgroups based on baseline characteristics will only be performed for cohort A. The number of participants in cohort B is considered too small to provide reliable results for subgroups.

Subgroup analyses for ORR and PFS (see [Section 2.6.6.2](#), [Section 2.8.1.4](#)) to assess the homogeneity of the treatment effect across demographic and baseline disease characteristics will be performed for the following subgroups (based on the FAS):

- a. Age (< 65 years vs. \geq 65 years)
- b. Gender (male vs. female)
- c. ECOG status (0 vs. 1)
- d. Smoking status (never smoker vs. combination of current smoker and former smoker)
- e. STK11 mutation status (yes vs. no)
- f. KEAP1 mutation status (yes vs. no)
- g. Presence of brain metastases at baseline based on BIRC assessment (yes vs. no)
- h. Race (Asian vs. Non-Asian)

Subgroup 5: Baseline characteristics subgroups for safety

Key safety analyses will be repeated on safety set for the following subgroups. The objective for carrying out these subgroup analyses is to identify potential safety issues that may be limited to a subgroup of participants, or safety issues that are more commonly observed in a subgroup of participants.

- a. Age (< 65 years vs. \geq 65 years)---
- b. Gender (male vs. female)
- c. ECOG status (0 vs. 1)
- d. Smoking status (former vs current vs never)
- e. STK11 mutation status (yes vs. no)
- f. KEAP1 mutation status (yes vs. no)
- g. Presence of brain metastases at baseline based on BIRC assessment (yes vs. no)
- h. Race (Asian vs. Non-Asian)

The following safety summaries will be performed by subgroup:

- AEs, regardless of study treatment, by preferred term and maximum CTC grade
- AEs with suspected relationship to study drugs by preferred term and maximum CTC grade

